### 10.6.2 Severe injection site reactions

Based on the SC mode of administration of high doses of protein and on a higher incidence of local injection site reactions observed at the highest dose level (300 mg weekly) in dupilumab studies, severe injection site reactions, are considered as a potential risk. Patients who experience an injection site reaction must be closely monitored for the possibility of a more intense injection site reaction with a future injection. Any severe injection reaction that lasts over 24 hours will be reported as an AESI with immediate notification. ADA and PK samples will be collected near the onset and completion resolution of the AESI for any additional analysis.

Prophylactic treatment/premedication for an injection site reaction is not permitted.

### 10.6.3 Infections, including opportunistic and parasitic infections

Some immuno-modulating biologics have been associated with an increased risk of infection, including opportunistic infection. Though dupilumab has not been shown to increase the frequency of severe or serious infections in general, as a precautionary measure, the Investigator

is required to carefully monitor for any signs or symptoms of infection such as, but not limited to, increased body temperature, malaise, weight loss, sweats, cough, dyspnea, pulmonary infiltrates, or serious febrile systemic illness.

Since dupilumab binds to IL-4R $\alpha$ , preventing IL-4 and IL-13 binding and activation of their respective receptors, it inhibits the Th2 cytokines productions. Infections with a diversity of helminthic parasites elicit eosinophilia via stimulation of Th2-like lymphocyte responses. The TH2 response is characterized by production of IL-4 and IL-5, subsequently generating IgG1 [Immunoglobulin Gamma 1] and IgE-secreting cells, and eliciting eosinophilia. Eosinophilia is prominent in a number of helminthic parasitic diseases. The eosinophilic response to helminths is determined both by the host's immune response and by the parasite, including its distribution, migration, and development within the infected host. Therefore patient with treatment of dupilumab may potentially have an increased risk of parasitic infection.

Infections defined in [Section 10.4.1.3](#) should be reported as AESIs within 24 hours.

A complete diagnostic work-up should be performed (ie, cultures, histopathological or cytological evaluation, antigen detection and serum antibody titers). Patients should be referred to an infectious disease specialist if deemed necessary for diagnostic work up and appropriate treatment.

Infections or infestations that do not respond to medical treatment should have study drug discontinued until the infection is resolved.

For any opportunistic infection, such as tuberculosis or other infections whose nature or course may suggest an immunocompromised status (See [Appendix I](#)), patients must be permanently discontinued from study medication.

In order to minimize this risk, any patient with an active parasitic infection is excluded from the study. Similarly, patients with suspected parasitic infection, or those at high risk of parasitic infection are also excluded, unless clinical and (if necessary) laboratory assessments have ruled out active infection before randomization. During the study, appearance of signs or symptoms (such as abdominal pain, cough, diarrhea, fever, fatigue hepatosplenomegaly) that could be associated with a parasitic infection should be carefully evaluated, especially if there is a history of parasitic exposure through recent travel to/ or residence in endemic areas, especially when conditions are conducive to infection (eg, extended stay, rural or slum areas, lack of running water, consumption of uncooked, undercooked, or otherwise potentially contaminated food, close contact with carriers and vectors, etc.). Subsequent medical assessments (eg, stool exam, blood tests, etc.) must be performed in order to rule out parasitic infection/infestation. Confirmed parasitic infections during the study should be reported as AESI with immediate notification.

#### **10.6.4 Elevated liver function tests**

No pre-clinical or clinical data has suggested any hepatic toxicity of dupilumab; however, as a general consideration of clinical development, the administration of immunosuppressant or immunomodulating agents may represent an additional risk factor for hepatotoxicity.

In order to closely follow liver function tests (LFT), assessment of total protein, albumin, total bilirubin, ALT, aspartate aminotransferase, and alkaline phosphatase are measured as part of the

clinical laboratory testing. Clinical laboratory testing at V1 adds hepatitis screen (HBsAg, HBsAb, HBcAb, HCVAb. Active hepatitis or patients with positive or indeterminate HBsAg, HBcAb or positive HCVAb at V1 are excluded from the study.

Guidance for the investigation of elevated LFTs is provided in [Appendix G](#).

## **10.7 ADVERSE EVENTS MONITORING**

All events will be managed and reported in compliance with all applicable regulations, and included in the final CSR.

## 11 STATISTICAL CONSIDERATIONS

### 11.1 DETERMINATION OF SAMPLE SIZE

The sample size is chosen to enable an adequate characterization of the efficacy between dupilumab 300 mg q2w (pooled A and B arms) and placebo with regard to the 2 co-primary endpoints, changes from baseline in NC and NPS at Week 24.

The observed mean NC reduction of the dupilumab group with qw dosing in ACT12340 is 0.95 and the observed mean NC reduction of the placebo group is 0.26. To calculate power, a conservative estimate is used that assumes the placebo-adjusted NC reduction of the dupilumab 300 mg q2w group is 80% of the dupilumab 300 mg qw group, the mean NC reduction of the dupilumab 300 mg q2w group is then assumed to be  $0.81 = 0.8 * (0.95 - 0.26) + 0.26$ . Assuming normal distribution of the change in NC, a common standard deviation (SD) of 1.03, which has incorporated a 20% inflation from the observed SD in ACT12340, and a 25% dropout rate, with 240 patients for the q2w pool and 120 patients in placebo, the study will have 99% power to detect an effect size of 0.534 using a two-sided test with  $\alpha = 0.05$  for the change in NC at Week 24 in the dupilumab 300 mg q2w group.

The observed mean NPS reduction of the dupilumab group with qw dosing in ACT12340 is 1.85 and the observed mean NPS reduction of the placebo group is 0.30. Using same conservative approach that assumes the placebo-adjusted NPS reduction of the dupilumab 300 mg q2w group is 80% of the dupilumab 300 mg qw, the mean NPS reduction of the dupilumab 300 mg q2w group is then assumed to be  $1.54 = 0.8 * (1.85 - 0.30) + 0.30$ . Assuming normal distribution of the change in NPS, a common standard deviation (SD) of 2.11, which has incorporated a 20% inflation from the observed SD in ACT12340, and a 25% dropout rate, with 240 patients for the q2w pool and 120 patients in placebo, the study will have 99% power to detect an effect size of 0.588 using a two-sided test with  $\alpha = 0.05$  for the change in NPS at Week 24 in the dupilumab 300 mg q2w group.

Therefore, with a sample size of 240 patients for the q2w pool ( Arm A and B) at Week 24, the combined power of the two co-primary efficacy endpoints is at least 98% for dupilumab 300mg q2w group with  $\alpha = 0.05$  assuming no negative correlation between the 2 endpoints.

The observed mean LMK reduction of the dupilumab group with qw dosing in ACT12340 is 9.07 and the observed mean LMK reduction of the placebo group is 0.23. Using same conservative approach that assumes the placebo-adjusted LMK reduction of the dupilumab 300 mg q2w group is 80% of the dupilumab 300 mg qw, the mean LMK reduction of the dupilumab 300 mg q2w group is then assumed to be  $7.30 = 0.8 * (9.07 - 0.23) + 0.23$ . Assuming normal distribution of the change in LMK, a common standard deviation (SD) of 5.50, which has incorporated a 20% inflation from the observed SD in ACT12340, and a 25% dropout rate, with 240 patients for the q2w pool and 120 patients in placebo, the study will have 99% power to detect an effect size of 1.285 using a two-sided test with  $\alpha = 0.05$  for the change in LMK at Week 24 in the dupilumab 300 mg q2w group.

Therefore, with a sample size of 240 patients for the q2w pool ( Arm A and B) at Week 24, the combined power of the three co-primary efficacy endpoints for Japan is at least 97% for dupilumab 300mg q2w group with  $\alpha = 0.05$  assuming no negative correlation between the 3 endpoints.

The sample size is also chosen to enable an adequate characterization of the efficacy between dupilumab 300 mg q2w (pooled A and B arms) and placebo with regard to the key secondary endpoints at Week 24, the change from baseline in the TSS, UPSIT score, the daily loss of smell assessment, the LMK, and the SNOT-22 scores, as well as the proportion of patients receiving SCS and/or planned to undergo surgery for nasal polyps.

Assuming the proportion of patients receiving SCS for NP and/or planned to undergo surgery for NP is 15% in the placebo group, and is 5% in the dupilumab group, with 240 patients for the q2w pool and 120 patients in placebo, the study will have 87% power to detect a hazard ratio of 0.316 between the treatment groups using a two-sided log rank test with  $\alpha = 0.05$ .

With 240 patients for the q2w pool and 120 patients in placebo, the study will have greater than 99% power to detect difference between the treatment groups for all other five key secondary endpoints at Week 24, using a similar assumption procedure as the change from baseline in NC and NPS at Week 24.

The sample size calculations were performed using nQuery Advisor 7.

## **11.2 DISPOSITION OF PATIENTS**

Screened patients are defined as any patient who signed the informed consent.

Randomized patients consist of all patients who have been allocated a treatment kit based on a randomization process. It will consist of all patients with a treatment kit number allocated and recorded in IVRS/IWSR database, and regardless of whether the treatment kit was used or not.

Patients treated without being randomized will not be considered as randomized and will not be included in any efficacy population.

## **11.3 ANALYSIS POPULATIONS**

### **11.3.1 Efficacy populations**

The population considered for the efficacy analysis will be the intent-to-treat (ITT) population.

#### ***11.3.1.1 Intent-to-treat population***

ITT population: all randomized patients analyzed according to the treatment group allocated by randomization regardless of whether the treatment kit is used or not.

### **11.3.2 Safety population**

The population considered for safety analysis will be the safety population.

Safety population: all patients exposed to study medication, regardless of the amount of treatment administered. The safety analyses will be conducted according to the treatment patients actually received.

Treatment emergent period for the safety population is defined as the time between the first administration of study medication to Week 12 of post treatment period.

In addition:

- Nonrandomized but treated patients will be part of the safety population.
- Randomized patients for whom it is unclear whether they took the study medication will be included in the safety population as randomized.

### **11.3.3 Systemic drug concentration population**

The systemic drug concentration population will consist of all patients in the safety population with at least one evaluable functional dupilumab concentration result. Patients will be analyzed according to the treatment actually received.

### **11.3.4 Anti-drug antibody population**

The anti-drug antibody population will consist of all patients in the safety population with at least one evaluable ADA serum sample that was assayed successfully in the ADA assay following the first dose of the study medication. Patients will be analyzed according to the treatment actually received.

### **11.3.5 Nasal biomarker substudy population**

Selected clinical sites will participate in a substudy for the collection of nasal samples and evaluation of biomarkers of inflammation.

## **11.4 STATISTICAL METHODS**

### **11.4.1 Extent of study treatment exposure and compliance**

The extent of study treatment exposure and compliance will be assessed and summarized according to actual treatment received within the safety population.

#### ***11.4.1.1 Extent of investigational medicinal product exposure***

Duration of IMP exposure is defined as: last dose date – first dose date + 14 days, regardless of unplanned intermittent discontinuations.

### **11.4.1.2 Compliance**

A given administration will be considered noncompliant if the patient did not take the planned dose of treatment as required by the protocol. No imputation will be made for patients with missing or incomplete data.

Percentage of compliance for a patient will be defined as the number of administrations the patient was compliant divided by the total number of administrations the patient was planned to take during the treatment period (ie, from the 1st to the last administration).

Treatment compliance, above-planned and under-planned dosing percentages will be summarized descriptively (N, Mean, SD, Median, Min, and Max). The percentage of patients with compliance is <80% will be summarized. In addition, number and percentage of patients with at least 1 above planned dosing administration will be given, as well as the number and percentage of patients with 0, (0, 20%], and >20% under-planned dosing administrations.

### **11.4.2 Analyses of efficacy endpoints**

#### **11.4.2.1 Analysis of co-primary efficacy endpoint(s)**

##### *11.4.2.1.1 Co-Primary efficacy variables*

The 2 co-primary efficacy variables are: change from baseline in NC and in NPS at Week 24. These variables will be assessed for dupilumab 300 mg q2w (pooled A and B arms) versus placebo (Arm C), respectively.

For Japan only, in addition to the 2 co-primary endpoints above, the following will also be a co-primary endpoint:

- Change from baseline in sinus opacifications assessed by CT scans using the LMK score at Week 24.

The following null hypothesis and alternative will be tested for pooled dupilumab arms against placebo:

- H0: No treatment difference between the dupilumab dose regimen and placebo.
- H1: There is a treatment difference between the dupilumab dose regimen and placebo.

##### *11.4.2.1.2 Analysis of the co-primary efficacy variables*

Each of the 2 co-primary efficacy endpoints (3 co-primary efficacy endpoints for Japan) will be analyzed using a hybrid method of the worst-observation carried forward (WOCF) and the multiple imputation (MI). With this approach, for patients who undergo surgery for NP or receive SCS for any reason, data collected postsurgery or post SCS will be set to missing, and the worst postbaseline value on or before the time of surgery or SCS will be used to impute missing Week 24 value (for patients whose postbaseline values are all missing, the baseline will be used to impute). For patients who discontinue the treatment without being rescued by surgery or receiving

SCS, a multiple imputation approach will be used to impute missing Week 24 value, and this multiple imputation will use all patients who have not been rescued by surgery or receiving SCS at Week 24 and data collected after treatment discontinuation will be included in the analysis. Each of the imputed complete data will be analyzed by fitting an ANCOVA model with the baseline covariate and factors for treatment, asthma status, prior surgery history, and regions. Statistical inference obtained from all imputed data will be combined using Rubin's rule. Descriptive statistics including number of subjects mean, standard error, and least squares (LS) means will be provided. In addition, difference in LS means and the corresponding 95% confidence intervals (CI) will be provided along with the p-values.

#### *11.4.2.1.3 Sensitivity analyses*

The reason and pattern of missing data will be carefully examined and tipping point analyses and other sensitivity analyses will be performed. Details of the sensitivity analyses will be provided in the SAP.

#### *11.4.2.1.4 Subgroup analysis*

To assess the consistency in treatment effects across different subgroup levels, subgroup analyses will be conducted for the co-primary efficacy endpoints with respect to age group, gender, region, prior surgery history, race, INCS dose level, baseline NPS, baseline NC, baseline TSS, baseline LMK, prior SCS use, and asthma comorbidity/NERD. The details will be provided in the SAP.

### **11.4.2.2 Analyses of key secondary efficacy endpoints**

#### *11.4.2.2.1 Analysis of the change from baseline in TSS, UPSIT score, the daily loss of smell assessment, the LMK, and SNOT-22 scores at Week 24 for dupilumab 300 mg q2w versus placebo*

The change from baseline in TSS, SNOT-22, UPSIT score, daily loss of smell, LMK score at Week 24 will be assessed for dupilumab 300 mg q2w (pooled A and B arms) versus placebo and will be analyzed using the hybrid method of the WOCF and the MI in the same fashion as for the co-primary endpoints.

Note: LMK will not be a secondary endpoint for Japan as it is already a co-primary endpoint.

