## **8.2.2 Rescue treatment**

During the study treatment period and off treatment follow-up, based on clinical evaluation, in case of worsening of signs and/or symptoms requiring medical intervention, the Investigator may consider rescue treatment with:

- Nasal lavage with saline and/or systemic antibiotics (up to 2 weeks in case of acute infection).
- Short course OCS (prednisone or prednisolone up to 2 weeks).
- Sino-nasal surgery for nasal polyps. Based on previous observations from PoC study, 8 weeks of IMP treatment is recommended prior to surgery to allow onset of treatment effect.

Patients receiving rescue treatment other than surgery during the study should continue on study drug unless the Investigator decides to withdraw the study treatment. Before starting treatment with SCS patients should come to the study site for the clinical assessments including endoscopy and PROs.

For patients who undergo or are planned for surgery for NP the Investigator may decide to continue IMP up to the time of surgery or end of treatment whichever date comes first (see [Section 9.2.1.5](#) for details). At the time of surgery patients will be permanently discontinued from study treatment and assessed as soon as possible using the procedures normally planned for the end-of-treatment (EOT) Visit as described in [Section 10.3.1](#).

In any case patients who prematurely discontinued the treatment will be encouraged to return to the study site for the efficacy and safety assessments planned at EOT visit and for additional visits as described in [Section 10.3.1](#).

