### **3. Lund-Mackay score**

For Japan, in addition to the two co-primary endpoints above, the following will also be a co-primary endpoint:

The LMK system is based on localization with points given for degree of opacification: 0 = normal, 1 = partial opacification, 2 = total opacification. These points are then applied to the maxillary, anterior ethmoid, posterior ethmoid, sphenoid, frontal sinus on each side. The OC is graded as 0 = not occluded, or 2 = occluded deriving a maximum score of 12 per side. This scoring system has been validated in several studies (29, 30, 31).

For patients in whom the OC is missing (because of a previous surgery) the reader should consider the location of the former OC and provide a scoring (as if the OC was there).

CT scan should be performed anytime during the run-in period before a first administration of IMP and at Visit 8 (Week 24). Whenever possible a cone beam CT scan should be utilized. In countries for which a specific approval procedure for the CT scan is required by a different committee than the local independent ethic committee (IEC)/institutional review board (IRB), patients may be enrolled using a CT available in the previous year or perform an MRI of the sinuses between V1 and V2. These countries will be exempted from all the planned study CT scans until approval from these committees is received. A Week 52 CT scan may be performed if approved by local ethics committees in order to assess the change from baseline to Week 52 using the 2 different treatment regimens of dupilumab 300 mg q2w for up to Week 52 and dupilumab 300 mg q2w/q4w up to Week 52.

Details for CT will be available in a separate operational manual provided to the sites.

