### 10.3.1 Permanent treatment discontinuation with investigational medicinal product(s)

Permanent treatment discontinuation is any treatment discontinuation associated with the definitive decision from the Investigator or the patient not to re-expose the patient to the IMP at any time.

Patients who discontinue treatment permanently during the treatment period will be assessed as soon as possible using all procedures normally planned for the End-of-treatment Visit with the exception of CT Scan. Patients who discontinue early during the post-treatment period will be assessed as soon as possible using all procedures normally planned for the end-of-study (EOS) Visit.

For patients in whom the surgery date is scheduled after the planned end of study, a follow up contact(s) should be performed around the time of planned surgery to document the surgery date. Surgery data will be collected only until e-CRF Closure and EOS will not be delayed.

Patients will also be instructed to:

- Return to the study site for evaluations of NPS, SNOT-22, at:
  - Week 24, Week 52: If the ETD visit occurred between Week 0-Week 16,
  - Week 52: If the ETD visit occurred between >Week 16-Week 40,
  - Week 64 (EOS): If the ETD visit occurred between >Week 40-Week 52.
- Return and have a CT Scan performed as scheduled at Week 24 and 52.

Patients who discontinue prior to week 40 will have the following assessed through week 52, patients who discontinue after week 40 will have the following assessed through week 64:

- Perform PK and ADA sampling at the initially scheduled visits for these assessments
- Continue to complete the e-diary for nasal congestion, loss of smell daily symptom and anterior/posterior rhinorrhea evaluation
- Continue on MFNS stable dose but patients are not required to complete the INCS use daily in the e-diary after ETD.
- Advise patients with comorbid atopic conditions (such as asthma) not to adjust their treatment without consultation with their physicians.
- Report any AE up to the last scheduled visit (Week 52 or Week 64 depending on the discontinuation date).
- Contact the Investigator during the post treatment period up to the EOS visit if the symptoms worsen requiring medical attention.

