  mcmc impute=monotone;  
  var asthma surgery region treatment basenps chg4nps chg8nps  
  chg16nps chg24nps;  
run;
```

2. For each of the imputed dataset with monotone missing pattern in step 1, the remaining missing data will be imputed using the regression method for the monotone pattern with adjustment for covariates including treatment groups, region, asthma/NERD strata, surgery strata and baseline value of the response variable.

```
proc mi data=dat_mc nimpute=1 seed=14280 out=dat_mi;  
  by _imputation_;  
  class asthma surgery region treatment;  
  monotone method=reg;  
  var asthma surgery region treatment basenps chg4nps chg8nps chg16  
  nps chg24nps;  
run;
```

3. Each of the 40 imputed datasets will be merged with the one dataset imputed by WOCF approach, and then be analyzed using the main statistical model. These 40 imputed datasets will be saved.

```
%macro w1;  
  %do i=1%to 40;  
    data wocf&i.;  
    set wocf;  
    _imputation_=&i.;  
    run;  
  %end;  
  data wocf_all;  
  set %do j=1 %to 40; wocf&j. %end;;  
  run;  
%mend w1;  
  
%w1  
  
data dat_imp;  
  set dat_mi wocf_all;  
Run;  
  
proc sort data=dat_imp;  
  by _imputation_;  
run;  
  
proc glm data= dat_imp;  
  by _imputation_;  
  class region asthma surgery treatment;  
  model = chg24nps = basenps asthma surgery region treatment;  
  lsmeans treatment / stderr;  
  estimate 'Diff Dupilumab vs Placebo' treatment -1 1;  
  ods output LSMeans=implsmeans Estimates=implsmeandiff;  
run;
```

4. Applying Rubin's rule to combine analysis results (point estimates and standard errors) from 40 imputations using PROC MIANALYZE for the LS means and difference in LS means between dupilumab and placebo. Sample code:

```
proc sort data=implsMeans; by trt01pn _imputation_;run;

proc mianalyze data= implsmeans;
  by trt01pn;
  modeleffects lsmean;
  stderr stderr;
  ods output ParameterEstimates=lsmeans;
run;

proc mianalyze data=implsmeandiff;
  modeleffects estimate;
  stderr stderr;
  ods output ParameterEstimates=lsmeandiff;
run;
```

Sensitivity analysis

For all sensitivity approaches, for patients who undergo surgery for NP or receive SCS for any reason, data collected post surgery or post SCS will be set to missing

Mixed-effect model with repeated measures (MMRM) approach

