2.4.4.2 Analyses of key secondary efficacy endpoints

2.4.4.2.1 Analysis of the change from baseline in LMK, TSS, UPSIT score, the daily loss of smell assessment, and SNOT-22 scores at Week 24 for dupilumab 300 mg q2w versus placebo

The change from baseline in LMK TSS, SNOT-22, UPSIT score, daily loss of smell at Week 24 will be assessed for dupilumab 300 mg q2w (pooled A and B arms) versus placebo and will be analyzed using the hybrid method of the WOCF and the MI the same as the primary approach of the co-primary endpoints. Descriptive statistics including number of patients, mean, standard error, and least squares (LS) means will be provided. In addition, difference in LS means and the corresponding 95% confidence intervals (CI) will be provided along with the p-values.

Note: LMK will not be a secondary endpoint for Japan as it is already a co-primary endpoint.

2.4.4.2.2 Analysis of the change from baseline in NPS, NC and SNOT-22 at Week 52

The change from baseline in NPS, NC and SNOT-22 at Week 52 will be assessed respectively for dupilumab 300 mg q2w (Arm A) and dupilumab 300 mg q2w/q4w (Arm B) versus placebo (Arm C) (Note treatment has three levels: Arm A, B and C) and will be analyzed using the hybrid method of the WOCF and the MI in the same way as the primary analysis approach for NC and NPS except at Week 52 instead of Week 24.

Descriptive statistics including number of patients, mean, standard error, and least squares (LS) means will be provided. In addition, difference in LS means and the corresponding 95% confidence intervals (CI) will be provided along with the p-values.

2.4.4.2.3 Analysis of proportion and time-to-event of patients requiring rescue treatment defined as: use systemic corticosteroids or NP surgery (actual or planned) during the treatment period for dupilumab 300 mg q2w versus placebo

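### For LMK at Week 24 the planned multiple imputation has no interim LMK to draw on and repeats the ANCOVA covariates; adding the NPS and NC data already collected would make it informative

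*Protocol*

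**What the plan says.** - **Method.** Protocol 11.4.2.2.1 says LMK, with the other Week 24 key secondaries, "will be analyzed using the hybrid method of the WOCF and the MI in the same fashion as for the co-primary endpoints". SAP 2.4.4.2.1 repeats this as "the hybrid method of the WOCF and the MI the same as the primary approach of the co-primary endpoints".
- **Imputation model.** The only code in SAP 2.4.4.1 is for NPS. Its variable list begins "var asthma surgery region treatment basenps chg4nps chg8nps" and goes on to the Week 16 and Week 24 changes. The text names treatment, region, asthma/NERD, surgery and the baseline value as covariates. No variable list is given for LMK.
- **Analysis model.** The ANCOVA in SAP 2.4.4.1 uses the same five terms.
- **CT schedule.** Protocol 1.2 and 9.1 place CT in run-in and at Week 24, with an optional scan at Week 52. After early discontinuation the patient is assessed "using all procedures normally planned for the End-of-treatment Visit with the exception of CT Scan", but is asked to "Return and have a CT Scan performed as scheduled at Week 24 and 52".
- **Rescue.** Under protocol 8.2.2, "Before starting treatment with SCS patients should come to the study site for the clinical assessments including endoscopy and PROs"; CT is not named. Values after surgery or systemic steroids are set to missing and replaced by the worst earlier post-baseline value, or by baseline if there is none (protocol 11.4.2.1.2).
- **Standing of LMK.** It is a co-primary endpoint for Japan, and elsewhere the first secondary in the SAP 2.4.4.3 hierarchy.

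**The concern.** Multiple imputation improves on a complete-case analysis when the imputation model holds something about the missing patient that the analysis model does not. For NPS that is the earlier visits. For LMK nothing is left. A non-rescued patient without a Week 24 CT would be imputed from baseline LMK and design factors alone, even if endoscopy and the diary had shown no response up to Week 16.

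At stake is the accuracy of the LMK estimate if missing CTs are related to response, and whether the SAP says clearly what will be done for this endpoint. The trial's ability to reach significance on LMK is not at stake.

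**Working it through.** **1. The plan's own figure.** From protocol 11.1: difference 0.8 × (9.07 − 0.23) = 7.07, SD 5.50, standardized effect 1.285, 240 versus 120 patients, 25% dropout. Completers are 180 and 90, so the standardized SE is √(1/180 + 1/90) = 0.129. Then 1.285/0.129 ≈ 9.95, and power exceeds 99.9%, consistent with the stated 99%. The figure already rests on completers, so losing interim information does not alter it.

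**2. What is available up to Week 24** (protocol 1.2)

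| Measure | Scheduled post-baseline values |
|---|---|
| NPS | Weeks 4, 8, 16, 24 |
| NC | daily |
| SNOT-22 | Weeks 4, 8, 16, 24 |
| UPSIT | Weeks 2, 4, 16, 24 |
| LMK | Week 24 only |

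**3. Imputation model against analysis model.** Taking the interim terms out of the NPS code leaves baseline, treatment, asthma/NERD, surgery and region. The ANCOVA has the same five. Imputing the outcome from the covariates of the analysis model returns the complete-case coefficients plus Monte Carlo noise.

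A simulation confirms this. Settings: 240 versus 120 patients; 25% of non-rescued patients missing at random; LMK figures as above; baseline mean 18, SD 4 and slope −0.4 assumed.

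| Non-rescued patients, no rescue in the trial | Complete-case ANCOVA | MI |
|---|---|---|
| 40 imputations, 400 runs | −7.123 (SE 0.685) | −7.126 (SE 0.689) |
| 1,000 imputations, 60 runs | −7.014 (SE 0.687) | −7.014 (SE 0.689) |

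**4. Rescued patients.** With no earlier post-baseline LMK, the worst-value rule falls back to baseline, so the change is 0. As an illustration, take the 5% and 15% rescue proportions in protocol 11.1. They are stated for a slightly different event, so the proportion that triggers the rule may differ. The expected difference is 7.30 × 0.95 − 0.23 × 0.85 = 6.935 − 0.196 = 6.74, against 7.07. In the same simulation the full hybrid gave −6.73, and complete-case ANCOVA in non-rescued patients gave −7.06.

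**5. Possible bias.** Suppose that in one arm a missing CT depends on NPS change through a logistic model. The completer mean for LMK in that arm then shifts by

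bias = ρ × SD × m,

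where ρ is the correlation of LMK change with Week 16 NPS change and m is the shift in mean standardized NPS change among patients with a CT. The values of ρ (0.3 to 0.7), the logistic slope (0.7 or 1.5) and the one-arm mechanism are assumptions; SD is 5.5.

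| Missing | Slope | m | Bias, ρ = 0.3 to 0.7 | Share of 7.07 |
|---|---|---|---|---|
| 10% | 0.7 | 0.067 | 0.11 to 0.26 | 1.6% to 3.6% |
| 10% | 1.5 | 0.122 | 0.20 to 0.47 | 2.8% to 6.6% |
| 25% | 0.7 | 0.161 | 0.27 to 0.62 | 3.8% to 8.8% |
| 25% | 1.5 | 0.277 | 0.46 to 1.07 | 6.5% to 15.1% |

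A simulation of the 25% case (1,500 replicates) gave 0.24 to 1.08. The direction depends on which arm is affected, and an equal mechanism in both arms cancels. With NPS change in the imputation model the simulated bias was within 0.03 of zero, with SE 0.65 to 0.74 either way.

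**The case against.** The case for leaving the plan alone is substantial.

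- **The restriction is inferred.** The code is labelled as a sample and is written for NPS; nothing forbids auxiliary variables for LMK. This stands, and it is a reason to write the list down.
- **A reader might infer that the whole LMK analysis is a complete-case ANCOVA.** It is not. Rescued patients stay in at zero change, and step 4 shows that the estimate moves by about 0.3 points. Failure that leads to rescue is already counted.
- **A reader might infer that missing patients are set to the arm mean.** The SAP imputes by regression on baseline and the design factors.
- **A reader might infer that nothing guards against informative missing CTs.** SAP 2.4.4.1 plans tipping-point and copy-increment analyses for all three Japan co-primaries, LMK included. The remaining gap is narrower: no LMK sensitivity analysis is stated where LMK is a key secondary. The MMRM adds little for LMK, which has one post-baseline visit up to Week 24.
- **25% missing is an upper bound.** Early stoppers are asked back for the Week 24 CT, data after discontinuation are used, and rescued patients are not multiply imputed. Some CTs will be absent through national approval exemptions, which do not depend on response.
- **Week 52 is different.** The Week 24 LMK is then an interim value, so the argument does not carry over.

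All of this limits the size of the point. None of it explains why recorded NPS and NC should be left out.

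**Conclusion.** The point holds as a cheap improvement to a valid analysis. Applied to LMK as written, the MI step is equivalent to complete-case ANCOVA in non-rescued patients, and the worst-value rule becomes baseline carried forward for patients rescued before the Week 24 CT. The analysis is sound if missingness depends only on baseline LMK, treatment, asthma/NERD, surgery and region.

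The bias could be about 0.1 to 0.5 points at 10% missing and about 0.25 to 1.1 points at 25%, against 7.07. These ranges rest on the assumed correlation, slopes and one-arm mechanism; with the same mechanism in both arms the bias is near zero.

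It would be wrong to infer that the LMK test is in danger. The worst simulated case leaves 7.07 − 1.08 = 5.99 at SE 0.74, a z of about 8. What is affected is the credibility of the estimate for a Japan co-primary and the first-listed SAP secondary, and the completeness of the pre-specification.

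**What to change.** In SAP 2.4.4.1 and 2.4.4.2.1:

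1. Give the variable list for imputing Week 24 LMK. To the present covariates add baseline and Week 4, 8, 16 and 24 values of NPS and of the 28-day NC average, with values after steroids or surgery set to missing as already planned.
2. Leave the ANCOVA and the worst-value rule as they are, and state that for LMK at Week 24 that rule is in effect baseline carried forward.
3. For Week 52, name the Week 24 LMK as the interim value; further auxiliaries are optional.

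The cost is a few lines of SAP text, a longer variable list in the imputation code and a slightly larger imputation model. No new data are needed. There may be a small gain in precision: with an assumed residual correlation of 0.7 between LMK change and an interim measure, the simulated SE fell from about 0.685 to 0.643.
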